10.6 Archiving of study documents

The Investigator follows the principles outlined in the CSA.

10.7 Study timetable and end of study

Planned treatment duration in the study is 13 weeks. will notify investigators when recruitment is complete. The end of the entire study is defined as 'the last visit of the last patient undergoing the study'.

The study may be terminated at individual centers if the study procedures are not being performed according to GCP, or if recruitment is slow. The entire study prematurely if concerns for safety arise within this study or in any other study with dapagliflozin.

11 DATA MANAGEMENT BY

Data Management

Data management will be performed by Center staff. Data will be entered in the WBDC system at the study site. Trained site staff will be responsible for entering data on the observations, tests and assessments specified in the protocol into the WBDC system. Data entered in the WBDC system will be immediately saved to a central database and changes tracked to provide an audit trail. The data will then be source data verified, reviewed/queried and updated as needed. The Principal Investigator is responsible for electronically signing the eCRF. Data queries will be raised for inconsistent, improbable or missing data. All entries to the study database will be available in an audit trail. The data will be frozen and then locked to prevent further editing. When all data have been coded, validated, signed, and locked, a clean file will be declared. Any treatment revealing data may thereafter be added and the final database will be locked. A copy of the eCRF will be archived at the study site when the study has been locked.

12 STATISTICAL METHODS AND SAMPLE SIZE DETERMINATION

12.1 Description of analysis sets

12.1.1 Efficacy analysis set

Intention to treat (ITT) is defined as all patients who have been randomized to study treatment and completed at least one follow-up where the KCCQ and NTproBNP are collected. The ITT data set will be used for the primary and secondary efficacy endpoints and exploratory endpoints.

12.1.2 Safety analysis set

All patients who received at least 1 dose of randomized dapagliflozin or placebo, and for whom post-dose data are available, will be included in the safety analysis set. Throughout the safety results sections, erroneously treated patients (eg, those randomized to dapagliflozin but actually given placebo) will be accounted for in the actual treatment group. If a patient received study drug from the wrong kit for only a part of the treatment duration and then switched to another, the associated actual treatment group for that patient will be the treatment group the patient had the longest exposure to.

12.2 Methods of statistical analyses

All analyses will be on the ITT unless otherwise specified. Baseline demographic and clinical data will be described between treatment and placebo study arms as mean ± standard deviation for continuous variables and compared using Student's T-test. Whereas discrete variables will be represented as a number and (%) and compared using the χ^2 or Fisher's exact test, as applicable.

The time course of continuous variables will be presented using standard descriptive summary statistics calculated at each scheduled measuring time point and the last individual measuring time point. Moreover, standard descriptive summary statistics will be calculated for the change (absolute or percent) from baseline to each scheduled measuring time point after baseline and the last individual measuring time point.

Due to the large number of study sites and the expected low number of patients per site it will not be appropriate to explore site effects.

Statistical significance will be defined using two-sided tests with α =0.05, unless otherwise specified. All statistical analyses will be performed by the **Statistical analyses** Department of Biostatistics using SAS version 9.4 (SAS Institute, Cary, North Carolina).

12.2.1 Primary variable

There are two co-primary efficacy endpoints:

- 1. Difference in mean NTproBNP between the treatment and placebo study arms at 6 and 12 weeks.
- Proportion of patients that achieve a meaningful change from baseline in quality of life (≥ 5pts increase in KCCQ overall summary score) or NTproBNP (≥ 20% decrease) over 12 week treatment period between dapagliflozin 10 mg and placebo.

The first co-primary endpoint of this study is to compare dapagliflozin versus placebo on mean NTproBNP at 6 and 12 weeks. A generalized linear mixed model with a compound symmetry covariance structure to estimate the average effect over 6 and 12 weeks controlling for baseline NTproBNP. Gamma distribution and log link function will be used because of the skewness nature of NTproBNP. Center is included as a random factor to account for clustering of patients within centers.

The second co-primary endpoint, proportion of patients with $a \ge 5$ point KCCQ overall summary score increase or $a \ge 20\%$ decrease in NTproBNP at 6 or 12 weeks will be analyzed using Mantel-Haenszel test controlling for center.

Both co-primary endpoints will be analyzed in the entire patient cohort, and then within the subgroups of patients with and without diabetes (as pre-specified subgroup analyses).

Statistical significance will be determined using an ordered testing procedure; the alpha will be 0.05 for hypothesis 1. If hypothesis 1 is rejected then hypothesis 2 will be tested at α =0.05 level. However, if hypothesis 1 is not rejected hypothesis 2 will not be tested.

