1.3 Sample Size and Power

Planned Sample Size	• Approximately 110 patients will be enrolled in each arm.
Power Statement	• The first dual primary endpoint of this study is the average of 6- and 12- week NT pro-BNP. A generalized linear mixed model with patient as a random effect will be used to estimate the average effect over 6 and 12 weeks controlling for baseline NT pro-BNP and other pre-specified covariates. A gamma distribution with log link will be used to account for the skewed nature of NT pro-BNP. Several sensitivity analyses will be performed, one of which includes site as a random effect to account for clustering of patients within centers. For the first dual primary endpoint a sample size of 110 for each group will achieve 80% power with α =0.05 to detect a difference in NT pro-BNP between the two groups of at least 302 pg/mL from baseline to 12 weeks. The assumptions for this calculation were derived from the BATTLESCARRED trial where the estimated standard deviation for NT pro-BNP was 1250 pg/mL. We expect the standard deviation in the DEFINE-HF Trial to be somewhat lower (961 pg/ml) given lower NT pro-BNP threshold. Of note, 302pg/mL reduction in NT pro-BNP is equivalent to 31.5% of the standard deviation in NT pro-BNP (based on the above assumption). There is an anticipated non-completion rate of approximately 13% so the final sample size per group will be 125.
	 The second dual primary endpoint, the proportion of patients with a ≥ 5-point KCCQ overall summary score increase or a ≥ 20% decrease in NT pro-BNP, averaging over 6 and 12 weeks, will be analyzed using generalized linear mixed models controlling for baseline NT pro-BNP and KCCQ overall summary score as well as several additional covariates as specified below. A binomial distribution with logit link will be used. Several sensitivity analyses will be performed, one of which includes site as a random effect to account for clustering of patients within centers. Power was determined based on comparisons of proportions between two independent groups, where the anticipated control group percent change is 30%. A sample size of 110 for each group will achieve 80% power with α=0.05 to detect an absolute difference in proportions between the two groups of 18% from baseline to 12 weeks for the second dual primary endpoint.

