2 GENERAL CONSIDERATIONS FOR DATA ANALYSES

2.1 Analysis Data Sets

Efficacy and safety analyses will be performed on data from the following analysis sets:

- Enrolled patients set (EPS) will consist of all patients who signed the informed consent. This data set will be used to summarize the patient disposition data.
- Modified intention to treat set (modified ITTS) is defined as all patients who have been randomized to study treatment, have received at least one dose of study medication, and have sufficient evaluable data for endpoint ascertainment during follow up. For clarity, patients with no evaluable data for a particular outcome during follow up will be excluded from the analyses of these respective endpoints. In patients who undergo initiation of intravenous home inotropic support and/or receive left ventricular assist device or heart transplant during the study or who are started on a prohibited medication (open label SGLT-2is), for efficacy analyses, the last available data point(s) prior to these events will be used. Subjects will be analyzed according to the randomization group. The modified ITTS data set will be used for the primary, secondary, and selected exploratory (NYHA class, loop diuretic dose) efficacy endpoints.
- On-treatment set (OTS) includes all subjects in the modified ITTS. Primary and secondary endpoint measurements will be excluded for the follow-up time point(s) when subjects were temporarily or permanently off the study drug at the time the corresponding measurements were obtained. The OTS data set will be used for a sensitivity analyses for the primary, secondary, and selected exploratory (NYHA class, loop diuretic dose) efficacy endpoints.
- The per protocol set (PPS) includes all subjects in the modified ITTS who did not have any major protocol deviations. Major protocol deviations, which are detailed in section 2.2, will be determined prior to unblinding of treatment groups. Subjects will be summarized according to actual treatment received regardless of the allocated treatment. This will be used for a sensitivity analysis for the primary efficacy endpoints only.

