5.1.1 The first dual primary endpoint: NT pro-BNP

Mean, standard deviation, median, and interquartile range (IQR) will be reported for NT pro-BNP and for its change from baseline at 6- and 12-week follow-up, for the entire cohort and by treatment group.

A generalized linear mixed model will be used to estimate the effect of treatment on the average of 6- and 12week NT pro-BNP values, adjusting for log baseline NT pro-BNP, history of DM, eGFR, and age. Random effects will be included for patient. A gamma distribution and log link function will be used to account for the skewed nature of NT pro-BNP. The model is as follows:

$$\begin{split} E(y_{ijk}) &= \mu_{ijk}, \qquad Var(y_{ijk}) = \mu_{ijk}^2 \varphi, \\ \log(\mu_{ijk}) &= \beta_0 + \beta_1 Trt_{ij} + \beta_2 t_k + \beta_3 Trt_{ij} * t_k + \beta x + \gamma_{ij}, \end{split}$$

$$\gamma_{ij} \sim N(0, \sigma^2),$$

where, μ_{ijk} denotes the expected NT pro-BNP level for patient j from site i at time k, Trt_{ij} is a 0/1 variable denoting treatment group (dapagliflozin vs. placebo), t_k indicates the follow-up assessment time ($t_6 = 0, t_{12} = 1$), and **x** is the design matrix for log baseline NT pro-BNP, age, DM, and baseline eGFR. γ_{ij} are patient random effects with variance σ^2 . ϕ is a scale factor. With this parameterization, the quantity $exp(\beta_1 + \beta_3/2)$ represents the expected relative effect of dapagliflozin vs. placebo on the geometric mean of 6- and 12-week NT pro-BNP. The quantities $exp(\beta_1)$ and $exp(\beta_1 + \beta_3)$ represent the corresponding relative effects at 6 and 12 weeks, respectively.

A sensitivity analysis will be performed using the same model additionally adjusting for AFib type (No AFib, persistent/permanent AFib, paroxysmal AFib) and baseline LVEF.

Additional sensitivity analysis will repeat the primary analysis but will also include site as a random effect to account for potential clustering by enrolling center. A different sensitivity analysis will use the same model as the primary analysis, but adjust only for the corresponding baseline measurements, without additional covariates.

Finally, another sensitivity analysis will repeat the primary analysis on the on-treatment set (OTS).

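### Protocol and SAP define the gatekeeping NT-proBNP test with different center terms, covariates and analysis sets, and the SAP is not consistent with itself

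*Protocol*

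**What the plan says.** **Model.** Both documents use a gamma model with log link and estimate an average effect over weeks 6 and 12. Protocol 12.2.1 fits it "to estimate the average effect over 6 and 12 weeks controlling for baseline NTproBNP", with compound symmetry, and adds "Center is included as a random factor to account for clustering of patients within centers". SAP 5.1.1 fits it "adjusting for log baseline NT pro-BNP, history of DM, eGFR, and age. Random effects will be included for patient". Site enters only in a sensitivity analysis that "will also include site as a random effect to account for potential clustering by enrolling center"; SAP 1.3 and 2.3 say the same.

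**Analysis set.** Protocol 12.1.1 takes randomized patients who "completed at least one follow-up where the KCCQ and NTproBNP are collected". SAP 2.1 takes randomized patients who "have received at least one dose of study medication, and have sufficient evaluable data for endpoint ascertainment during follow up", judged outcome by outcome. For patients who start home inotropes or an open-label SGLT-2 inhibitor, or who receive an LVAD or transplant, it uses only data from before the event. Protocol 12.1.1 has neither the dose condition nor the cut-off.

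**Role of the test.** Under protocol 12.2.1 the second primary endpoint is not tested if the first fails. Under SAP 2.5 it is then tested, but only as exploratory. In both, this one test decides whether the second endpoint is confirmatory.

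**The concern.** The lead test of a trial should have one definition. Here a reader with both documents finds two models and two populations for it. The differences are not cosmetic. One model accounts for clustering by center and the other does not. One adjusts for three more covariates. One population ends follow-up at events that are plausibly tied to worsening heart failure, so the values removed may be informative. At stake are the P value that opens or closes the gate, and the ability of an outside reader to confirm that the reported analysis was the planned one.

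**Working it through.** **1. Is the protocol model anywhere in the SAP?** The analyses of the first endpoint that bear on center and covariates are:

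| Analysis | Center/site | Covariates beyond baseline NT-proBNP |
|---|---|---|
| Protocol 12.2.1 primary | random | none |
| SAP 5.1.1 primary | absent | diabetes history, eGFR, age |
| SAP site sensitivity | random | diabetes history, eGFR, age |
| SAP baseline-only sensitivity | absent | none |
| SAP extended sensitivity | absent | those three plus AFib type, LVEF |

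No SAP row matches the first. Compound symmetry and a patient random intercept serve a similar purpose, so the conflict lies in center, covariates and population.

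**2. Are the sets nested?** Read literally, no. A patient followed up but never dosed is in the protocol set and outside the SAP set. A patient with follow-up NT-proBNP but no KCCQ is in the SAP set for this endpoint and outside the protocol set. The SAP's on-treatment and per-protocol sets are drawn from the modified ITT set, and 9.2 item 4.4.1 applies the SGLT-2 inhibitor cut-off to all three. So no SAP analysis uses every observed value.

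**3. Is the SAP one specification?** Not quite. SAP 2.6 adds baseline KCCQ to the first-endpoint model; 5.1.1 does not. SAP 9.2 item 6.8 drops patients with missing gender, AFib type or LVEF from both primary analyses. None of these is a listed covariate of either primary model, although gender is needed to compute eGFR (SAP 2.7).

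**4. Type I error.** Each model is valid alone. An illustrative simulation used 220 patients, 30 sites, a normal log-scale outcome, baseline correlation 0.7, three covariates explaining 3% of variance, a center share of variance of 0 to 0.10 and 2,000 runs per case. All of these except the patient and site numbers are assumptions. Each model rejected in 4.3% to 5.8% of null trials. The two disagreed in 2.4% to 4.8% of null trials and in 6.1% to 9.5% of trials at about 80% power.

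Suppose the better of the two results were taken. For two two-sided 5% tests with correlation ρ, the error is 1 − P(|Z₁| < 1.96 and |Z₂| < 1.96):

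- ρ = 0.98: 5.9%
- ρ = 0.95: 6.5%
- ρ = 0.90: 7.0%

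The simulation gives the same quantity as (rejection rate A + rejection rate B + disagreement)/2. The lowest is (4.45 + 4.30 + 2.65)/2 = 5.7%, at a center share of 0.02. The highest is (5.75 + 5.60 + 4.75)/2 = 8.05%, at 0.10.

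**5. Precision lost by omitting site.** If arms were balanced within each site, the reported standard error would be too large by 1/√(1 − ICC): 1.010, 1.026 and 1.054 at ICC 0.02, 0.05 and 0.10. Neither document states that randomization is stratified by site. With unstratified allocation of 218 patients to 30 sites, comparing the model with and without site gives about 0.1%, 0.6–0.7% and 2.1–2.4%. At the top of that range, 1.024² = 1.049, or about 5% of the sample size. Neither document gives an ICC.

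**The case against.** The strongest reply is that a SAP may refine a protocol, and that this SAP names one primary model for the endpoint and labels the others as sensitivity analyses. That largely stands. A reader might infer that the trial's type I error is 6–7%. The documents do not support this: that rate requires someone to run a model that the SAP does not contain and then report the better result, and nothing suggests this was intended. SAP 2.2 also fixes exclusions of patients and data before unblinding, although it does not cover the choice of model.

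A reader might also infer that dropping center costs 1–5% in precision. That holds only with within-site balance, which the documents do not state. Both documents note the low number of patients per site, and the SAP still runs a site model, so clustering is examined.

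Nor can one conclude that no text says which document governs. The SAP's opening pages were not in the text available here, and a precedence statement there cannot be ruled out.

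Finally, the population differences are probably small. Drug is dispensed at randomization, other SGLT-2 inhibitors are prohibited, and planned LVAD or transplant within 90 days of screening is an exclusion. This is fair, but the documents give no expected counts. What the reply does not remove is the mismatch itself, the SAP's disagreement with its own sections 2.6 and 9.2, and the absence of any analysis on all observed values.

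**Conclusion.** The mismatch is real and should be corrected before unblinding, but it does not invalidate the test. Protocol and SAP differ on center, covariates and population for the gatekeeping endpoint, and following the SAP alone still leaves the covariates and the exclusions unsettled. Either model, fixed in advance, holds about 5% type I error. The figure of about 6–7% measures what an open choice would cost, under assumed correlations of 0.90 to 0.98. The loss of precision from omitting site is about 0.1–2.4%, for an assumed ICC of 0.02 to 0.10 and no balance within site. The effect of the dose condition and the data cut-off cannot be sized from the documents.

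**What to change.** Before unblinding, state one primary model and one analysis set in the same words in protocol 12.1.1 and 12.2.1 (and the synopsis) and in SAP 2.1, 2.6, 5.1.1 and 9.2 item 6.8, and record the reason for the change.

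- **Site:** primary model or sensitivity analysis are both acceptable if fixed in advance.
- **Baseline KCCQ:** settle whether it belongs in the first-endpoint model, and make SAP 2.6 and 5.1.1 agree.
- **Item 6.8:** exclude patients only for missing covariates that the primary model uses.
- **Added sensitivity analysis:** analyze the first primary endpoint in all randomized patients, using every observed NT-proBNP value regardless of later SGLT-2 inhibitor, inotropes, LVAD or transplant.

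The cost is wording in two documents and one extra model run, with no new data collection.

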12.2.2 Secondary variables

The following secondary efficacy variables have been identified:

- 3. Proportion of patients with $a \ge 5pts$ increase in KCCQ over 12 weeks
- 4. Proportion of patients with $a \ge 20\%$ decrease in NTproBNP over 12 weeks
- Proportion of patients with a ≥ 5pts increase in KCCQ and a ≥ 20% decrease in NTproBNP over 12 weeks
- 6. Change in KCCQ score over 12 weeks.
- 7. Change in 6 minute walk score over 12 weeks.
- 8. Difference in mean BNP at 6 and 12 weeks.
- 9. Change in HbA1c over 12 weeks. (evaluated separately in patients with and without type 2 diabetes)
- 10. Change in weight over 12 weeks
- 11. Change in systolic blood pressure over 12 weeks

For secondary analyses proportional comparisons will be analyzed using the same testing method as the primary analyses. For continuous variable comparisons an analysis of covariance (ANCOVA) model including terms for treatment group and baseline covariate. The ANCOVA model will be used to derive the treatment difference with 95% confidence interval and corresponding two-sided p-value. Additionally, the mean change within each treatment group will be calculated with corresponding 95% confidence intervals.

Secondary endpoints will be analyzed in the entire patient cohort, and then within the subgroups of patients with and without diabetes (as pre-specified subgroup analyses).

12.2.3 Exploratory variables

The following exploratory variables have been identified:

- 1. Effects on average weekly loop diuretic dose (furosemide equivalent).
- 2. Effects on the rate of hospitalizations for heart failure.
- 3. Effects on rate of urgent outpatient heart failure visits.
- 4. Effects on the rate of hospitalizations for heart failure and urgent outpatient heart failure visits.
- 5. Change in NYHA Class over 12 weeks.
- 6. Change in NTproBNP and KCCQ at 6 weeks from baseline and 12 weeks from baseline.
- 7. Effect on lung fluid volumes measured by remote dielectric sensing ReDS[™] (SensiVest) over the treatment period.
- 8. Change in mean lung fluid volumes measured by remote dielectric sensing ReDSTM (SensiVest) between week 12 and week 13.

Exploratory data will be summarized descriptively and presented by treatment group. Exploratory endpoints will be analyzed in the entire patient cohort, and then within the subgroups of patients with and without diabetes (as pre-specified subgroup analyses).

12.2.4 Safety variables

The safety evaluations will include the analyses of all AEs of special interest and SAEs, however the following safety variables have been identified *a priori*:

- 1. All cause death
- 2. Cardiovascular death
- 3. Non-fatal myocardial infarction (MI)
- 4. Stroke
- 5. Acute kidney injury (defined as doubling of serum creatinine based on the RIFLE criteria)
- 6. Volume Depletion
- 7. Severe hypoglycemic events
- 8. Ketoacidosis

Safety data will be summarized descriptively and presented by treatment group.

12.2.5 Analysis for safety

Safety analyses will be done periodically during the study and reported to the IDSMC. A formal IDSMC charter will be developed.

12.3 Determination of sample size

For the first co-primary endpoint a sample size of 110 for each group will achieve 80% power with α =0.05 to detect a reduction in NTproBNP between the two groups of at least 302 pg/mL from baseline to 12 weeks. The assumptions for this calculation were derived from the BATTLESCARRED trial where the estimated standard deviation for NTproBNP was 1250 pg/mL. We expect the standard deviation in the DEFINE-HF Trial to be somewhat lower (961 pg/ml) given lower NTproBNP threshold. Of note, 302pg/mL reduction in NTproBNP is equivalent to 31.5% of the standard deviation in NTproBNP (based on the above assumption).

The second co-primary endpoint is a combined endpoint of $a \ge 5$ point KCCQ overall summary score increase or $a \ge 20\%$ decrease in NTproBNP. The sample size was determined using two independent groups where the anticipated control group percent change is 30%. A sample size of 110 for each group will achieve 80% power with α =0.05 to detect a difference in proportional change between the two groups of 18% from baseline to 12 weeks for the second co-primary endpoint.

There is an anticipated loss to follow-up of approximately 13% so the final sample size per group will be 125.

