The time course of continuous variables will be presented using standard descriptive summary statistics calculated at each scheduled measuring time point and the last individual measuring time point. Moreover, standard descriptive summary statistics will be calculated for the change (absolute or percent) from baseline to each scheduled measuring time point after baseline and the last individual measuring time point.

Statistical significance will be defined using two-sided tests with α =0.05, unless otherwise specified. All statistical analyses will be performed by the **Sector** Department of Biostatistics using SAS version 9.4 (SAS Institute, Cary, North Carolina).

The first co-primary endpoint of this study is to compare dapagliflozin versus placebo on mean NTproBNP at 6 and 12 weeks. A generalized linear mixed model with a compound symmetry covariance structure will be used to estimate the average effect over 6 and 12 weeks controlling for baseline NTproBNP. Gamma distribution and log link function will be used because of the skewness nature of NTproBNP. Center is included as a random factor to account for clustering of patients within centers.

The second co-primary endpoint, proportion of patients with $a \ge 5$ point KCCQ overall summary score increase or $a \ge 20\%$ decrease in NTproBNP at either 6 or 12 weeks, will be analyzed using Mantel-Haenszel test controlling for center.

For the first co-primary endpoint a sample size of 110 for each group will achieve 80% power with α =0.05 to detect a reduction in NTproBNP between the two groups of at least 302 pg/mL from baseline to 12

weeks. The assumptions for this calculation were derived from the BATTLESCARRED trial where the estimated standard deviation for NTproBNP was 1250 pg/mL. We expect the standard deviation in the DEFINE-HF Trial to be somewhat lower (961 pg/ml) given lower NTproBNP threshold. Of note, 302pg/mL reduction in NTproBNP is equivalent to 31.5% of the standard deviation in NTproBNP (based on the above assumption).

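### The stated 80% power for NT-proBNP at 110 per group does not follow from the stated inputs: a two-sample comparison gives about 64%, and nothing stated supports 80% for the planned model

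*Protocol*

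**What the plan says.** Protocol 12.3 states that "a sample size of 110 for each group will achieve 80% power with α =0.05 to detect a reduction in NTproBNP" of at least 302 pg/mL between the groups from baseline to 12 weeks. On the spread it says: "We expect the standard deviation in the DEFINE-HF Trial to be somewhat lower (961 pg/ml) given lower NTproBNP threshold". The source trial's SD was 1250 pg/mL. The section equates 302 pg/mL with 31.5% of the assumed SD, expects about 13% loss to follow-up and sets 125 per group.

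The synopsis makes the same claim ("For the first co-primary endpoint a sample size of 110 for each group will achieve 80% power"), as does SAP 1.3 ("a sample size of 110 for each group will achieve 80% power with α =0.05 to detect a difference in NT pro-BNP"). SAP 1.3 also says "Approximately 110 patients will be enrolled in each arm", although its power statement ends at 125 per group.

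Protocol 12.2 fixes the sidedness: "Statistical significance will be defined using two-sided tests with α =0.05, unless otherwise specified". Protocol 12.2.1 gives hypothesis 1 the full 0.05, with hypothesis 2 tested only if hypothesis 1 is rejected.

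The planned analysis is a gamma, log-link mixed model used "to estimate the average effect over 6 and 12 weeks controlling for baseline NTproBNP". In SAP 5.1.1 the target quantity "represents the expected relative effect of dapagliflozin vs. placebo on the geometric mean of 6- and 12-week NT pro-BNP".

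**The concern.** The power paragraph gives a difference, an SD, an alpha, a group size and a power. These five values determine one another for a comparison of two means, and here they disagree. The paragraph names no method. It gives no baseline or between-visit correlation, no residual variance, and no mean or variance on the log scale. A reader therefore cannot tell whether the 80% is a miscalculated two-sample figure or a figure for the planned model whose assumptions were left out.

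The scale differs too. Power is stated for an absolute pg/mL difference to week 12, while the SAP model estimates a ratio of geometric means over weeks 6 and 12. A pg/mL SD cannot be carried to that scale without further inputs.

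This is the only power justification for the first primary endpoint, so the risk of a false negative on that endpoint is not known from the plan. That risk also bears on the second endpoint. If the first is not significant, the second is not tested (Protocol 12.2.1) or becomes exploratory with a nominal P value (SAP 2.5).

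**Working it through.** **Inputs.** Difference 302 pg/mL, SD 961 pg/mL and 110 per group (synopsis, Protocol 12.3, SAP 1.3); alpha 0.05, two-sided (Protocol 12.2); no alpha split (Protocol 12.2.1).

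**Step 1: try to reproduce 80%.** The standardised difference is d = 302/961 = 0.314 (the plan's 31.5% is this figure, loosely rounded).

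Normal approximation: power = Φ(d·√(n/2) − 1.960) = Φ(0.3143 × √55 − 1.960) = Φ(2.331 − 1.960) = Φ(0.371) = 64.5%. The noncentral t gives 64.1%.

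Variants built from the plan's own numbers (noncentral t):

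| Variant | Power |
|---|---|
| Two-sided, 110 per group, d = 0.315 | 64% |
| Two-sided, 125 per group | 70% |
| One-sided, 110 per group | 75% |
| One-sided, 125 per group | 79.8% |
| Two-sided, 110 per group, SD 1250 | 43% |

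Only the one-sided calculation at 125 comes close to 80%. It contradicts both the two-sided rule and the stated 110.

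**Step 2: what 80% would need.** With 1.960 + 0.842 = 2.802:

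- Group size: 2 × (2.802/0.3143)² = 159 per arm (t: 160).
- Detectable difference at 110 per arm: 2.802 × 961 × √(2/110) = 363 pg/mL (t: 365).
- SD at which 302 pg/mL and 110 per arm give 80%: 302/(2.802 × √(2/110)) = 799 pg/mL (t: 796). Neither document states such an SD.
- Equivalent variance factor relative to 961²: (799/961)² = 0.692 (t: 0.686).

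**Step 3: could the planned model supply that reduction?** This step is a linear approximation on the pg/mL scale. It assumes that 961 is a single-visit SD, equal at all visits. Let r be the correlation of baseline with each follow-up visit and rho the correlation between weeks 6 and 12. Neither is in the documents, so the values below are assumptions. The variance of the baseline-adjusted mean of two visits, relative to 961², is (1 + rho)/2 − r².

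Example: rho = 0.8 and r = 0.5 give 0.90 − 0.25 = 0.65, hence power of about 82%.

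Power at 110 per arm (noncentral t):

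| rho | r = 0.3 | r = 0.5 | r = 0.7 |
|---|---|---|---|
| 0.7 | 76% | 85% | 97% |
| 0.8 | 73% | 82% | 95% |
| 0.9 | 71% | 79% | 93% |

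Reaching 80% needs r of at least about 0.41 at rho = 0.7, 0.46 at rho = 0.8 and 0.51 at rho = 0.9. If r = rho, the factor peaks at 0.5625 (at r = 0.25), so power is never below about 87%.

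**Step 4: numbers per arm.** 125 × 0.87 = 108.75. The 110 is therefore an evaluable count, while SAP 1.3 calls it an enrolment count.

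**The case against.** The NT-proBNP sentence does not name a two-sample test; in Protocol 12.3 only the second endpoint's calculation refers to two independent groups. The planned analysis is a baseline-adjusted, two-visit model, so the 64% belongs to an analysis the trial will not run. The scenarios below 80% also need baseline to correlate much more weakly with follow-up than the two follow-up visits correlate with each other. The visits at weeks 0, 6 and 12 are equally spaced. Under the same approximation, equal correlations give at least 87% and first-order autoregressive decay at least about 84%. On this view the defect is an unstated method. Replacing 80% with 64% could mislead, and a completed trial is better read from its confidence interval than from its planned power.

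Much of this stands. The planned model may well exceed 80%, and the 64% must not be presented as its power. The approximations are only indicative for a gamma, log-link model. A confidence interval will be the main guide to a finished result.

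The objection does not rescue the statement itself. The only spread and effect given are 961 and 302 pg/mL, and the plan links them as a fraction of an SD. Those inputs do not yield 80%, and no stated assumption bridges the gap.

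**Conclusion.** The point holds and should be fixed. On the stated inputs, a two-sided two-sample comparison has about 64% power, not 80%. Reaching 80% takes 159 to 160 per arm, or a difference of 363 to 365 pg/mL at 110 per arm. These figures rest only on numbers in the documents.

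The power of the planned model is unknown from the documents. Under the linear approximation it runs from about 71% to 97% over r from 0.3 to 0.7 and rho from 0.7 to 0.9, and it is above 80% for equal or autoregressive correlations. The conclusion is that the 80% is unsupported, not that the trial is too small. The remarks on the second endpoint's conditional power and on 110 versus 125 are minor and do not carry the conclusion.

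**What to change.** Keep the enrolment. In the synopsis, Protocol 12.3 and SAP 1.3:

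- **Preferred:** restate power for the planned gamma, log-link model on the ratio scale. Give the target ratio, the log-scale SD, and the assumed baseline and between-visit correlations, with a range of power over plausible values.
- **Otherwise:** replace 80% with about 64%, and give about 365 pg/mL as the difference detectable with 80% power. Label both as the unadjusted single-visit comparison of means, not as the power of the planned model.
- Add one sentence saying that the second endpoint's confirmatory power is conditional on significance for the first.
- In SAP 1.3, align the enrolment wording with 125 randomised and about 109 to 110 evaluable per arm.

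The cost is one recalculation and a wording change in each document. Enrolment, model, test and alpha do not change.
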